### 7.4 Anticipated Benefits

Potential benefits to the subjects may include, but are not limited to:

- relief of valvular pathology (aortic stenosis, and/or aortic regurgitation)
- improved hemodynamic performance

## Clinical Investigation Plan

- avoidance of long term anticoagulation therapy

In addition to these benefits, additional benefits may occur to future patients through experience gained in this clinical study.

### 7.5 Risk-to-Benefit Rationale

Patients who have a malfunctioning native or prosthetic aortic valve require intervention. Without intervention, patients whom have a malfunctioning aortic valve also will have a poor long-term prognosis with mortality rates that can exceed 50% by 5 years. Trifecta heart valves have been in commercial use since 2010 and provide a lifesaving technology for patients with few associated risks. These valves have an excellent safety profile. [REDACTED]

[REDACTED] As such, the benefits outweigh the risks associated with the use of the device and its components/materials.

## 8 Requirements for Investigator Records and Reports

### 8.1 Deviations from CIP

A deviation is defined as an instance(s) of failure to follow, intentionally or unintentionally, the requirements of the CIP. The investigator should not deviate from the CIP.

In some cases, failure to comply with the CIP may be considered failure to protect the rights, safety and well-being of subjects; such non-compliance exposes subjects to unreasonable risks. Examples: failure to adhere to the inclusion/exclusion criteria, failure to perform safety assessments intended to detect adverse events. Investigators should seek to minimize such risks by adhering to the CIP.

The PI must maintain accurate, complete, and current records, including documents showing the date of and reason for each deviation from the CIP. Relevant information for each deviation will be documented as soon as possible on the applicable CRF. The site will submit the CRF to the Sponsor.

The PI is required to adhere to local regulatory requirements for reporting deviations to IRB/EC.

Under emergency circumstances, deviations from the CIP to protect the rights, safety and well-being of subjects may proceed without prior approval of the Sponsor and the IRB/EC. Such deviations shall be documented and reported to the Sponsor and the IRB/EC as soon as possible.

### 8.2 Safety Reporting

Safety surveillance and the safety reporting by the investigator starts as soon as the subject is enrolled in this clinical study. Refer to Section 5.3 for the definition of subject enrollment.

The safety surveillance and the safety reporting will continue until the last study visit has been performed, the subject is deceased, the subject/investigator concludes his participation into the clinical study or the subject withdrawal from the clinical study.

The PI will report the event to the IRB/EC per their reporting requirements. The following are reportable events per this CIP (see Appendix B for definitions):

- Adverse Device Effects (regardless of seriousness)
- Serious Adverse Events (regardless of severity) including those specified in Edmunds Criteria which include:
  - Structural valve deterioration

## Clinical Investigation Plan

- Nonstructural dysfunction
- Embolism (valve related)
- Valve thrombosis
- Major bleeding event
- Endocarditis
- Death

The above events will be reported to the Sponsor. The Sponsor will ensure that all events are reported to the relevant authorities as per regulations. The sites should notify the Sponsor of reportable adverse events by creating and saving the applicable CRF within the electronic data capture (EDC) system.

The investigator should report all SAEs to the Sponsor as soon as possible but no later than outlined below.

Clinical Site	Reporting timelines
All Sites	SAEs must be reported to the Sponsor no later than 3 calendar days from the day the study personnel became aware of the event or as per the investigative site's local requirements, if the requirement is more stringent than those outlined.

The date the study staff became aware the event met the criteria of an SAE must be recorded in the source document. The Investigator will further report the SAE to the local IRB/EC according to the institution's IRB/EC reporting requirements.

Adverse events will be monitored until they are adequately resolved or the subject has ended his/her participation in the trial, whichever comes first. The status of the subject's condition should be documented at each visit.

Records relating to the subject's subsequent medical course must be maintained and submitted (as applicable) to the Sponsor until the event has subsided or, in case of permanent impairment, until the event stabilizes and the overall clinical outcome has been ascertained. Adverse events will be monitored until they are adequately resolved. The status of the subject's condition should be documented at each visit.

The following information should be collected for each event:

- Date AE occurred
- Date the site, PI, became aware of the event
- Main symptoms of the event
- Treatment
- Seriousness
- Relationship to device
- Resolution status

Additional information may be requested, when required, by the Sponsor in order to support the reporting of AEs to regulatory authorities.

The PI must notify the IRB/EC, if appropriate, in accordance with national and local laws and regulations, of the AEs reported to the Sponsor.

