#### 5.10.2 Clinical Events Committee (CEC)

An independent CEC will be established for the study to provide review and adjudication of pre-defined clinical events (e.g. Edmunds Criteria events). The primary function, responsibilities and membership of the CEC will be described in detail in a CEC charter.

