### Embolism

Embolism is any embolic event that occurs in the absence of infection after the immediate perioperative period (when anesthesia-induced unconsciousness is completely reversed). Only arterial emboli will be captured. Pulmonary emboli, cardiac mural thromboemboli and atherosclerotic particle emboli are not to be reported. Subsets of embolic events are:

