#### Systemic Embolic Event:

An operative, autopsy or clinically documented embolus that produced symptoms from complete or partial obstruction of a peripheral (non-cerebral) artery. Systemic events should be classified as:

- Minor: symptoms resolve completely without medical or surgical intervention
- Major: permanent injury or medical/surgical intervention required
- Fatal: death results as a consequence of the embolism or from related adverse events (less than or equal to 30 days or during the same course of hospitalization)

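### Protocol 8.2 leaves a non-serious embolism that the site judges unrelated to the valve without a clear route to the Sponsor or the events committee, although Appendix B counts it as an embolism

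*Protocol*

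**What the plan says.** Protocol 8.2 names two reportable groups and sends the reader to Appendix B for definitions. The first is "Adverse Device Effects (regardless of seriousness"). The second is "Serious Adverse Events (regardless of severity) including those specified in Edmunds Criteria", followed by a list of the Edmunds events. In that list embolism appears as "Embolism (valve related"); no other item carries a condition of this kind. Sites notify the Sponsor of reportable events by CRF, and "Relationship to device" and seriousness are among the items collected for each event.

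Appendix B opens its definition with "Embolism is any embolic event that occurs in the absence of infection after the immediate perioperative period" and adds "Only arterial emboli will be captured". It then removes pulmonary emboli, cardiac mural thromboemboli and atherosclerotic particle emboli from reporting. Its subsets include TIA, RIND and a class of systemic embolism described as "Minor: symptoms resolve completely without medical or surgical intervention".

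On adjudication, Protocol 5.10.2 says "An independent CEC will be established for the study to provide review and adjudication of pre-defined clinical events", gives the Edmunds events as the example, and leaves the details to a charter. SAP 3.2 summarizes all reported adverse events by seriousness and relationship, and separately all events adjudicated by the committee (CEC).

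**The concern.** The list and the definition it refers to differ in scope. The list asks for emboli related to the valve, under a heading for serious events. The definition asks about source, timing and infection, and it covers mild events. A site following 8.2 must decide whether a mild embolic event is valve related before it knows whether to report it. That attribution is the kind of question an independent CEC is meant to settle.

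Safety is part of the study objective (Protocol 4.2), and thromboembolism and stroke are listed as anticipated device effects (Protocol 7.1.1). If about 35 sites apply the filter differently, the adjudicated embolism count is incomplete to an unknown degree, varies by site for reasons unrelated to the valve, and does not match the study's own definition. Competing explanations for a TIA are foreseeable, since subjects having concomitant atrial fibrillation ablation are eligible (Protocol 4.4).

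**Working it through.** No arithmetic applies. The check sets the texts side by side and classes each event by seriousness and by the site's view of relatedness.

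**Inputs.** The SAE definition in Appendix B requires death, a serious deterioration in health with one of the listed outcomes, a malignant tumor, or a fetal or congenital outcome. The ADE definition requires a relation to use of the device. The embolism item in 8.2 requires a relation to the valve. I treat these last two conditions as the same judgment by the site.

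**Two readings of 8.2.** The Edmunds list follows the word *including* under the SAE bullet. Read strictly, an Edmunds event is reportable only if it is serious. Read leniently, every listed event is reportable in its own right.

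| Embolic event, as the site judges it | Strict reading | Lenient reading |
|---|---|---|
| Serious, related | SAE and ADE | SAE and ADE |
| Serious, unrelated | SAE | SAE |
| Non-serious, related | ADE | ADE and list item |
| Non-serious, unrelated | No route | No route: fails the qualifier |

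Three of the four combinations are covered on either reading. The fourth is covered on neither, because the lenient reading still leaves the valve-related condition on embolism.

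**Is the fourth combination empty?** No. A TIA is fully reversible within 24 hours, a RIND within three weeks, and a minor systemic embolism resolves without intervention. None of these need meet an SAE criterion. An example that survives the Appendix B exclusions is a TIA of undetermined source, managed as an outpatient, which the site does not attribute to the valve.

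**Do other sections supply a route?**
- Protocol 5.4.3, 5.4.4 and Table 2 collect adverse events at visits where applicable. They do not say that this overrides the scope set in 8.2.
- SAP 3.2 defines a category for non-serious events unrelated to device or procedure. That shows how such events would be tabulated if they arrive; it does not tell sites to send them.
- Protocol 5.10.2 defers to the CEC charter, which is not among the documents. A charter can say what is adjudicated, but nothing here describes a channel for events that sites are not asked to report.

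**Other Edmunds items.** Valve thrombosis and structural deterioration concern the study valve itself, so they would normally enter as ADEs even when mild. Non-serious bleeding judged unrelated is exposed on the strict reading only.

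**The case against.** The best case on the other side is that the qualifier is shorthand. Appendix B already excludes mural and atherosclerotic particle emboli, as well as infective and perioperative events, and its neurologic subsection speaks of events related to operated valves. On this view the list and the definition aim at the same events. Visits collect adverse events with no stated limit on seriousness or relatedness, the SAP expects non-serious unrelated events in the database, and the charter or CRFs may settle the rest.

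Part of this stands. The exclusions are real, so Appendix B does not count every arterial embolus. A TIA attributed to carotid plaque is not an example of the gap, and one attributed to atrial fibrillation is open to argument. The wording of 8.2 is ambiguous, and the charter could help.

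It does not close the gap. An exclusion by named source is not a test of valve-relatedness: an embolus of unknown source passes the first and can fail the second. The visit schedule and the SAP category do not clearly override the instruction that sites notify reportable events. If the SAP does expect these events, the mismatch with 8.2 is a further reason to clarify it.

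**Conclusion.** The inconsistency is real and narrow. A non-serious embolic event that falls outside the Appendix B exclusions and that the site judges unrelated to the valve has no clear route to the Sponsor or the CEC. This rests on the text of 8.2 and Appendix B, and on the assumption that the unseen charter and CRFs do not add a route.

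Several stronger conclusions might be inferred, and the documents do not support them:
- *Embolism is reportable only when valve related.* Any embolism that meets the SAE definition is reportable whatever its cause.
- *Mild events in general are lost.* Those judged device related are reportable as ADEs.
- *Understated embolism counts are then set against the literature.* Protocol 6.4 and SAP 2.7 plan that comparison for the primary endpoint only.
- *The main results are biased.* Embolism is neither the primary endpoint nor one of the five descriptive endpoints. Deaths are reported separately under Protocol 8.2.1, so the mortality endpoints are not directly affected. SAP 2.3 plans no hypothesis test.

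The documents give no rate for embolism, for its mild share, or for how often sites would judge such events unrelated. Any count of missed events would be a product of assumptions, so I give none. The consequence is limited to the completeness and between-site consistency of the summaries in SAP 3.2. The change is still worth making because it removes a filter ahead of independent adjudication at little cost.

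**What to change.** In Protocol 8.2:
1. Add a third reportable class, separate from ADEs and SAEs: *all events meeting the Appendix B Edmunds definitions, whether or not serious and whatever the site's view of relatedness*.
2. Delete the valve-related qualifier from the embolism item.
3. State that the CEC decides valve-relatedness and applies the mural and atherosclerotic source exclusions, and that sites report suspected embolic and neurologic events of any arterial source.

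The third step is needed because Appendix B currently tells sites not to report emboli from those sources. Left as it is, that sentence would keep a source attribution at the site even after the qualifier is gone. It should become an adjudication rule, and the CEC charter should be checked for agreement.

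The cost is a wording change, site training, a few more event forms and CEC cases, and a slightly higher reported embolism count.

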## Clinical Investigation Plan

### 8.2.1 Subject Death

All subject deaths are to be documented on the Death Form and reported to the Sponsor as soon as possible after becoming aware of the event.

The subject Death Form should always be accompanied with the relevant Adverse Event Form and relevant source documentation. In the event of a subject death, an autopsy should be performed whenever possible and the Trifecta GT valve explanted and returned to SJM for evaluation. If available, death summaries and autopsy reports should be provided to SJM.

### 8.2.2 Complaints

During the study, the investigator will be responsible for reporting all complaints. A complaint is defined as any written, electronic or oral communication that alleges deficiencies related to the identity, quality, durability, reliability, safety, effectiveness or performance of a device after it is released for distribution.

If the complaint involves an adverse event (AE), the investigator must complete an Adverse Event CRF, including the information on the complaint and submit to SJM as soon as possible.

If the complaint does not involve an AE, the investigator must notify the SJM Post Market Surveillance Department by submitting the information on the device via email to [REDACTED] as soon as possible after becoming aware of the complaint. This information will not be collected on a CRF for the study.

For study sites in the United States:

Should a subject death be caused by the SJM device or the device contributed to the death, the investigator should complete a Form 3500A (MedWatch) and submit to SJM and the FDA within 10 days after becoming aware of the event.

### 8.3 Source records

Source documents will be created and maintained by the site throughout the clinical study. The data reported on the CRFs will be derived from, and be consistent with, these source documents, and any discrepancies will be explained in writing.

### 8.4 Records Retention

The Sponsor and the Principal Investigators will maintain the clinical study documents as required. Measures will be taken to prevent accidental or premature destruction of these documents. The Principal Investigator or the Sponsor may transfer custody of records to another person/party and document the transfer at the study site or the Sponsor's facility, as appropriate.

These documents must be retained by the study site for a period of 2 years after the conclusion of the clinical study and made available for monitoring or auditing by the Sponsor's representative or representatives of the applicable regulatory agencies.

All original source documents must be stored for the maximum time required by the regulations at the hospital, research institute, or practice in question. If original source documents can no longer be maintained at the site, the investigator will notify the Sponsor.

## 9 Clinical Data Handling

The Sponsor will be responsible for the data handling. The Sponsor and/or its affiliates will be responsible for compiling and submitting all required reports to governmental agencies. Data will be analyzed by the

## Clinical Investigation Plan

Sponsor and may be transferred to the Sponsor's locations worldwide and/or any other worldwide regulatory authority in support of a market-approval application.

The PI or institution will provide direct access to source data during and after the clinical study for monitoring, audits, IRB/EC review and regulatory authority inspections. As required, the PI or institution will obtain permission for direct access to source documents from the subject, hospital administration and national regulatory authorities before starting the clinical study.

### 9.1 Protection of Personally Identifiable Information

SJM respects and protects personally identifiable information collected or maintained for this clinical study. The privacy of each subject and confidentiality of his/her information will be preserved in reports and when publishing any data. Confidentiality of data will be observed by all parties involved at all times throughout the clinical study. All data will be secured against unauthorized access.

### 9.2 Data Management Plan

A Data Management Plan (DMP) will describe procedures used for data review, database cleaning, and issuing and resolving data queries. If appropriate, the DMP may be updated throughout the clinical study duration. All revisions will be tracked and document controlled.

Subject data will be captured in a validated electronic data capture (EDC) system hosted by the Sponsor.

Only authorized site personnel will be permitted to enter the CRF data through the EDC system deployed by SJM. An electronic audit trail will be used to track any subsequent changes of the entered data.

### 9.3 Document and Data Control

#### 9.3.1 Traceability of Documents and Data

The investigator will ensure accuracy, completeness legibility and timeliness of the data reported to the Sponsor on the CRFs and in all required reports.

#### 9.3.2 Recording Data

The CRF will be reviewed by the authorized site personnel. An appropriate comment will be provided to explain changes to data reported on the CRF.

## 10 Monitoring

It is the responsibility of the Sponsor to ensure the clinical study is conducted, recorded and reported according to the approved CIP, subsequent amendment(s), applicable regulations and guidance documents.

Monitoring will be conducted according to SJM's Clinical Monitoring work instruction. Prior to beginning the clinical study, the Sponsor will contact the investigator or designee to discuss the clinical study and data requirements. A designated monitor will periodically review the subject records and associated source documents. The investigator shall make subject and clinical study records available to the clinical monitor for monitoring.

## Clinical Investigation Plan

### 11 Compliance Statement

#### 11.1 Statement of Compliance

This clinical study will be conducted in compliance with the most current regional and local laws and regulations. Principles of Good Clinical Practice will be followed as based on the most current version of the World Medical Association (WMA) Declaration of Helsinki.

The investigator will sign a Clinical Trial Agreement and agrees to be compliant with it. The investigator will not start enrolling subjects or requesting informed consent from any subject prior to obtaining IRB/EC approval and relevant Regulatory Authority approval, if applicable, and authorization from the Sponsor in writing for the clinical study. If additional requirements are imposed by the IRB/EC or relevant Regulatory Authority, those requirements will be followed. If any action is taken by an IRB/EC or a relevant Regulatory Authority with respect to the clinical study, that information will be forwarded to the Sponsor.

As the Sponsor, SJM has taken up general liability insurance in accordance with the requirements of the applicable local laws. An appropriate SJM country representative will be utilized to understand the requirements for the type of insurance that will be provided for subjects, and such information will be incorporated into the site informed consent, as applicable. If required, additional subject coverage or a clinical study specific insurance will be provided by the Sponsor.

#### 11.2 Quality Assurance Audits and Regulatory Inspections

The investigator and/or delegate should contact the Sponsor immediately upon notification of a regulatory authority inspection at the site. A monitor or designee will assist the investigator and/or delegate in preparing for the audit. The Sponsor may perform quality assurance audits, as required.

The Principal Investigator or institution will provide direct access to source data during and after the clinical study for monitoring, audits, IRB/EC review and regulatory authority inspections, as required. The Principal Investigator or institution will obtain permission for direct access to source documents from the subject, hospital administration and national regulatory authorities before starting the clinical study.

#### 11.3 Repeated and Serious Non-Compliance

In the event of repeated non-compliance or a one-time serious non-compliance, as determined by the Sponsor, a monitor or designee will attempt to secure compliance by one or more of the following actions:

- Visiting the investigator,
- Contacting the investigator by telephone,
- Contacting the investigator in writing,
- Retraining of the investigator.

If an investigator is found to be repeatedly non-compliant with the signed agreement, the CIP or any other conditions of the clinical study, the Sponsor will either secure compliance or, at its sole discretion, terminate the investigator's participation in the clinical study. In case of termination, the Sponsor will inform the responsible regulatory authority, as required, and ensure that the IRB/EC is notified, either by the Principal Investigator or by the Sponsor.

